S is the estimated value of the standard deviation between the two populations.

δ is the difference between the two averages.

The S and δ were the values of the MMSE scale decided by the researcher based on expert opinion (Liang Jingzhao, Zhi Yanmin, 2022), S= 2.75 , δ = 2.14. The level of significance (α) was 0.05, $t_{0.05/2}= 1.96$, β was 0.10, $t_{0.1}= 1.28$. By substituting the formula, 34 samples were required for each of the two groups.

An estimated 10% was added to the calculated sample size in anticipation of some missing data. The calculated sample size for this study was 76 patients (EG: 38 patients, CG: 38 patients).

8) Sampling method: Purposive sampling

9) Subject setting and participant

PHASE 1 (Delphi-method study for screening and recruitment)

The psychomotor rehabilitation nursing plan design will use Delphi-method which is an integration involving multiple expertise for the PMT development. The participants are the professionals with academic and/or practical experience in Neurology and cognitive training in China's hospitals or universities. There is no agreed method to consider someone an expert in a given field. To facilitate the selection process, it will use a simple point evaluation system. It will include all professionals with a final evaluation of at least 2 points. Regarding academic experience, it will consider the following factors: At least one publication on the

field of cognitive training (1 point) & at least one publication on the field of Neurology (1 point) OR at least one publication on the field of cognitive training in MCI (2 points). Concerning practical experience, it will consider experience in the development of a cognitive training program (1 point). Moreover, it will also consider if the professional had clinical experience in the application of cognitive training (1 point).

Purposive sampling. Potential participants will be identified through a literature review, existing academic contacts, and a web search for cognitive training programs (for MCI or Neurology or other conditions) and the respective scientific teams. After being evaluated in accordance to the point system previously described, professionals who met the inclusion criteria (2 points or more) will be invited to participate by email. In the initial questionnaire, they will be asked to recommend other professionals who they considered to be experts in the field. Recommended professionals who met the inclusion criteria will be contacted and invited to join the expert panel.

PHASE 2 (Quasi-Experimental design for PMT rehabilitation nursing interventional study)

This experimental method will be used in Quasi-Experimental Design (Non-randomized controlled trial) with experiment and control groups for comparison. Ethics consideration on older adults which would psychologically and emotionally impact in case not selected for experimental group. This research will be carried out in Liaoning Province of China. The rehabilitation nursing intervention will be carried out for older adults with MCI admitted in two China elderly care institutions which the name is Jinzhou Pension Comprehensive Service Center (JPCSC) and Jinzhou Rehabilitation Hospital (JRH). Because of ethical consideration on older adults for logistical and economical wise, easy to travel, practical, less budget. So the experimental group is JRH, and the control group is JPCSC. Purposive sampling, whereby older adults with MCI will be selected and invited to participate the study.

The PMT rehabilitation nursing intervention plan

From Table in the literature review, we can see that most interventions lasted for 3 months. Therefore, older adults will be engaged in a 12-week PMT rehabilitation nursing plan involving 2 phases of relaxation and breathing exercises, face exercises, hand exercises and mind exercises to promote cognitive health. The experimental group will be given interventions, twice a week every Tuesday and Thursday 9-10 am along with the study

intervention. Meanwhile, the control group will be given a standard health education on cognitive health.

Table The Mind-body Exercise of Psychomotor Rehabilitation Nursing Plan

Week	Phase	Intervention methods	Assessment
Week 0-6 Tuesday Thursday 9:00-10:00 am	Psychomotor function Phase 1	
1.Do relaxation and breathing exercises before and after exercise (10 minutes).
 
2.Blink alternately, bulge left and right cheeks, and improve facial motor function (10 minutes).
 
3.(10 minutes)
  
4.(10 minutes)
  
5.Carry out upper limb gymnastics exercises to improve limb motor function (20 minutes).
	Assessment time is at the baseline (before intervention).
Week 7-12 Tuesday Thursday 9:00-10:00 am	Psychomotor function Phase 2	
1. Do relaxation and breathing exercises before and after exercise (10 minutes).
 
2.(10 minutes)
  
3.(10 minutes)
	Assessment time is at the 12 week (after intervention).

		 
1. (10 minutes)
  
2. Carry out upper limb gymnastics exercises with music to improve limb motor function (20 minutes).
	
--	--	--	--

10) Data collection and Research tool

Phase 1: To develop and validate the psychomotor rehabilitation nursing plan through content/face validation using the Delphi Method for older adults with mild cognitive impairment.

The draft of the PMT rehabilitation nursing plan will be summarized through a literature review. An expert letter questionnaire will be formulated to make the PMT rehabilitation nursing plan more suitable for MCI older adults in China, and specialist consultation will be conducted face-to-face or by email, according to the actual situation. The Delphi method was used to reach a consensus on each program's characteristics, structure, and cognitive training tasks of the PMT rehabilitation nursing plan. A panel of experts was invited to participate in the content validation by answering two rounds of questions (scale and free-text boxes) regarding the program. Changes were made between the rounds according to the results of the first round. The consensus was defined as at least 70% of the experts agreeing on the validity of a characteristic. Experts will be invited to rate the importance and feasibility of the questionnaire items. The experts will be required to provide feedback to us within 2 weeks after receiving the questionnaire. After the first round of expert inquiry, the PMT

rehabilitation nursing program will be modified, deleted and supplemented based on the experts' scores and opinions on the items, so as to determine the second round of expert inquiry questionnaires and conduct the second round of expert inquiry. There will be a 3-week interval between the first and second rounds. After receiving the questionnaires from the experts, the inquiry results will be summarized and statistically analyzed until the experts' opinions reach a consensus, and the entire inquiry process will be terminated.

The duration of participant involvement in the Delphi method will be approximately 6 – 10 weeks in total, depending on the number of rounds required to reach expert consensus. Each Delphi round will require participants to complete the questionnaire, which is estimated to take 20 – 30 minutes per round. Between rounds, there will be a 1 – 2-week interval for data analysis and feedback preparation. While we anticipate achieving consensus within two rounds, a third or fourth round may be necessary if the responses require further refinement. In such a case, participants will be informed in advance, and their continued involvement will be requested. We will strive to minimize the burden on participants while ensuring robust and reliable results.

Phase 2: To evaluate the effectiveness of the psychomotor rehabilitation nursing plan among older adults with mild cognitive impairment.

The data will be collected from January 2025 to December 2025 in China's older adults care institutions. The data collection form was created by the researcher to record general information about older adults, such as age, gender, education level, family history of dementia, marital status, personal annual income, chronic disease. It will take no more than 5 minutes. Then, It will conduct questionnaire surveys before the intervention (baseline) and after the intervention (12 weeks). The questionnaires involved include MoCA, which has 11 questions and takes about 10 minutes; PANSS, which has 30 questions and takes about 20 minutes; HAMA-14, which has 14 questions and takes about 10 minutes; HAMD-17, which has 17 questions and takes about 15 minutes. All questionnaires will take no more than 60 minutes. Due to ethical issues, the names of the elderly participating in this study are only used for data collection, and their identity information will not be disclosed.

Data/Specimen handling:

1. Collection: Participant data will be collected through questionnaires and assessments during the study. No biological specimens will be collected as part of this research.

2. Storage and Security: All participant data will be anonymized and stored in a password-protected electronic database. Hard copies, if any, will be kept in a locked cabinet accessible only to the research team.
3. Usage: The data will be used exclusively for this study to evaluate the effectiveness of the psychomotor rehabilitation nursing plan. No secondary use of data will occur without additional consent from participants.
4. Retention and Destruction: Data will be retained for 5 years following the publication of the study findings, after which it will be securely destroyed by permanent deletion of digital files and shredding of hard copies.
5. Confidentiality: Participant confidentiality will be strictly maintained throughout the study. All identifiers will be replaced with unique codes to ensure privacy."

Research material: The materials used in PMT rehabilitation nursing intervention plan.

- i) Rehabilitation functional training hand coordinator
- ii) Rehabilitation training geometric figure cognitive plug-in board
- iii) Hand-eye-brain coordination training ball
- iv) Finger Function Dexterity Trainer
- v) Intelligence training puzzle board
- vi) Music for upper limb gymnastics exercises

1) Rehabilitation functional training hand coordinator

2) Rehabilitation training geometric figure cognitive plug-in board

3) Hand-eye-brain coordination training ball

4) Finger Function Dexterity Trainer

5) Intelligence training puzzle board

Questionnaire:

- i) Cognitive assessment:

The cognitive status of older adults was assessed by the Montreal Cognitive Assessment (MoCA) scale. Developed by Nasreddine et al. in Canada with reference to the MMSE, the MoCA evaluates multiple cognitive domains, including attention, executive function, memory, language, visuospatial skills, abstract thinking, calculation, and orientation, making it suitable for a comprehensive assessment of various types of cognitive impairment (Nasreddine ZS, 2005). In Western countries, a cutoff score of 26 is commonly used to identify MCI.

In China, various versions of the MoCA are available, including the Beijing, Changsha, and Cantonese versions, with the Beijing version being the most widely used. The cutoff scores of the MoCA Beijing version vary for different populations. According to a study by Lu et al. (2011) involving 8,411 community-dwelling older adults aged 65 years and above, the optimal cutoff scores for diagnosing MCI with the Beijing version are ≤ 13 for illiterate

individuals, ≤ 19 for those with primary education, and ≤ 24 for those with middle school education or higher. The sensitivity and specificity for identifying MCI were 80.5% and 82.5%, respectively.

ii) Psychological assessment:

The psychological of older adults was assessed by the Positive and Negative Syndrome Scale (PANSS), including the positive scale (7 items, 7~49 points), the general psychopathology scale (16 items, 16~112 points), and the negative scale (7 items, 7~49 points). The higher the score is, the worse the rehabilitation.

The reliability and validity of the Chinese version of PANSS have been verified (SI Tianmei et al. , 2004) and applied in clinical practice. The internal consistency reliability was 0.87(Cronbach α). The internal consistency reliability of the 5 dimensions ranged from 0.74 ~ 0.90. The structure, validity and reliability of PANSS (Chinese version) are acceptable.

iii) Emotional assessment:

The emotional assessment was assessed by the Hamilton Depression Rating Scale (HAMD-17) and the Hamilton Anxiety Rating Scale (HAMA-14), which are among the most widely used scales for evaluating emotional status. HAMA-14 contains two aspects; physical and mental. It includes 14 items with a total score of 56. HAMD-17 covers; despair, somatization symptoms, sleep disorders, and anxiety. It consists of 17 items with a total score of 52. (Maier, 1988; Maier, 1990). The 2025 Expert Consensus on Neuropsychological Assessment of Mild Cognitive Impairment (2025) recommends the use of these scales, as they effectively identify and quantify depressive and anxiety symptoms in patients with MCI. These tools have been widely adopted due to their high sensitivity and specificity, as well as their ease of administration and interpretation.

11) Data analysis

Objective No. 1 and 2 : To develop and validate the psychomotor rehabilitation nursing plan through content/face validation using the Delphi Method for older adults with mild cognitive impairment in promoting cognitive health.

Quantitative analyses will be conducted using SPSS version 28. The mean, standard deviation, coefficient of variation (CV), and full score ratio of all items will be calculated. The positive coefficient and authority coefficient (Cr) of the experts will be calculated. The

authority coefficient will equal to the mean value of the expert's self-assessed familiarity and the basis of expert judgment. The coordination degree of expert opinions will be expressed by Kendall's coordination coefficient (W). The P value < 0.05 will be considered to indicate statistical significance.

Expected result (Dummy Table): The Delphi-method of the PMT rehabilitation nursing plan

Table General information of experts

Items	Groups	Number of people	Composition ratio (%)
Gender	Male		
	Female		
Age (years)	30-40		
	40-50		
	> 50		
Education level	Undergraduate		
	Master		
Years of working experience	< 10		
	10-20		
	> 20		
Professional title	Intermediate		
	Senior		
Professional composition	Nursing		
	Neurology		
	Rehabilitation Medicine		
Province	Liaoning		
	Beijing		
	Shanghai		
	Guangzhou		

Table Specific data statistical results of each item in the first round of correspondence consultation

Item	Statements	Score (±)	CV	Consensus, n (%)
1. General Aspects of The PMT Rehabilitation Nursing Plan				
1.1 The Plan Structure	Older adults will be engaged in a 12-week PMT rehabilitation nursing plan involving 2 phases (twice a week every Tuesday and Thursday 9-10 am).			
1.2 Performance Sequence	All older adults will perform the same execution/performance sequence. The tasks must take place sequentially according to the pre-defined logic. In total, the plan comprises 5 distinct tasks in each phase.			

2. Description of The PMT Rehabilitation Nursing Plan				
2.1 Phase 1 -Task 1	Do relaxation and breathing exercises before and after exercise (10 minutes).			
2.2 Phase 1 -Task 2	Blink alternately, bulge left and right cheeks, and improve facial motor function (10 minutes).			
2.3 Phase 1 -Task 3	Hand-eye coordination training: The older adults followed instructions to grab the colorful beads with their hands and slide them along the curved track (10 minutes).			
2.4 Phase 1 -Task 4	Cognitive training puzzle board: The older adults put puzzle pieces of different colors and shapes into the corresponding grooves according to the instructions (10 minutes).			
2.5 Phase 1 -Task 5	Carry out upper limb gymnastics exercises to improve limb motor function (20 minutes).			
2.6 Phase 2 -Task 1	Do relaxation and breathing exercises before and after exercise (10 minutes).			
2.7 Phase 2 -Task 2	Hand muscle training/flexibility training/hand-eye coordination/improved circulation: The older adults held and rotated two balls with one hand according to instructions (10 minutes).			
2.8 Phase 2 -Task 3	Hand fine training/flexibility training/hand-eye coordination/endurance and concentration training (10 minutes).			
2.9 Phase 2 -Task 4	Hand-eye coordination training/cognitive ability training/fine skills training/teamwork and social interaction training (10 minutes).			
2.10 Phase 2 -Task 5	Carry out upper limb gymnastics exercises with music to improve limb motor function (20 minutes).			

Objective No. 3: To evaluate the effectiveness of psychomotor rehabilitation nursing plan in enhancing cognitive function among older adults with mild cognitive impairment.

Data entry and analysis will be performed using SPSS 28.0 software. Descriptive statistics will be used to summarize the general information of older adults. Numerical data will be presented as mean (SD) or median (IQR) based on their normality distribution. Categorical data will be presented as frequency (%). The comparison of scores of various scales are based on paired t-test statistical methods. The P value <0.05 will be considered to indicate statistically significant with 95% confidence interval (CI).

Expected result (Dummy Table): The effect assessment of the PMT rehabilitation nursing plan

Table Comparison of cognitive status between two groups ($\bar{x} \pm s$, scores)

Assessment	Before (n = 76)	After (n = 76)	Diff (95% CI)	t	P
Orientation					
Registration					
Attention and Calculation					
Recall					
Language and Praxis					
MoCA total score					

[figure not shown]
Table Comparison of psychological status between two groups ($\bar{x} \pm s$, scores)

Assessment	Before (n = 76)	After (n = 76)	Diff (95% CI)	t	P
Positive scale					
General psychopathology scale					
Negative scale					

Table Comparison of mental rehabilitation status between two groups ($\bar{x} \pm s$, scores)

Assessment	Before (n = 76)	After (n = 76)	Diff (95% CI)	t	P
Mood-related signs					
Behavioral disturbance					
Cyclic functions					
Ideational disturbance					

Study flowchart

Gantt chart & milestone

Research Activities	2024				2025				2026			
	Jan-Mar	Apr-Jun	Jul-Sep	Oct-Dec	Jan-Mar	Apr-Jun	Jul-Sep	Oct-Dec	Jan-Mar	Apr-Jun	Jul-Sep	Oct-Dec
Preliminary discussion												
Preparing research proposal												
Ethical application and approval from USM												
Data collection												
Data analysis and interpretation												
Thesis write-up and submission												

Ethical consideration

This study will require ethical approval from the Human Research Ethics Committee of USM (JePEM). The research activity will only be commenced after obtaining the ethical approval.

1) Subject vulnerability

i) Informed consent: Before beginning the questionnaire or interview, clearly explain the purpose, content, and participants' choices, ensuring that they fully understand their rights and know they can withdraw at any time without affecting their rights.

ii) Emphasize voluntary participation: Make it clear that participants are free to refuse to answer any questions and can withdraw from the interview or questionnaire at any point.

2) Declaration of absence of conflict of interest

i) Declaration of no conflicts of interest: I have not received any compensation, shares, or other forms of remuneration from any company or financial interest involved in the research, nor do I stand to gain any direct or indirect benefits from the research results. I am not subject to any external pressure, and all research activities, data analysis, and result reporting are based on scientific methods and objective judgment.

ii) Ensuring and maintaining the integrity of the research: Throughout the research process, I will maintain transparency. All data collection, analysis, and reporting will strictly adhere to scientific norms and standards, ensuring independence and freedom from external influences. I will follow the ethical guidelines set by academic and research institutions to ensure that no external parties influence the design, handling of data, interpretation of results, or reporting. If a potential conflict of interest arises at any stage of the research, I will immediately report it to the relevant institutions and implement appropriate measures, such as introducing independent oversight or review procedures, to eliminate or manage the conflict.

3) Privacy and confidentiality

The ethical issues considered in this study are related to older adults' confidential information and means of intervention and rehabilitation care. Because their personal information will be obtained and new rehabilitation care methods will be implemented. The names in older adults data will not be disclosed.

4) Community sensitivities and benefits

When designing questionnaires or interview questions related to cognitive impairment in the older adults, it is essential to minimize potential distress, anxiety. Avoid negative or potentially embarrassing wording, using neutral and respectful terms. For example, use "cognitive changes" instead of "cognitive impairment". Refrain from using stigmatizing terms such as "dementia", and opt for more neutral or supportive language like "memory issues" or "thinking difficulties". Ensure the environment in which the questionnaire is conducted is safe and stress-free, giving participants ample time to respond. Foster an atmosphere of respect, empathy, and care to reduce tension. If participants show signs of anxiety or distress during the interview, pause or stop the

session, check in with their feelings, and decide whether to continue based on the situation.

Direct benefits to participant: Participants may experience improvement in their cognitive function and overall mental health through participation in the psychomotor rehabilitation program. They will undergo regular health evaluations, which may help in identifying and addressing potential health issues early. Free access to the intervention program and related therapeutic activities may enhance their quality of life during the study period.

Indirect benefits to participant: The participants' involvement will contribute valuable data to the development of better care strategies for individuals with mild cognitive impairment. Their participation may increase awareness and understanding of MCI among themselves and their families, potentially leading to improved daily care practices. The findings of this study may have a positive impact on public health policies and future interventions for similar populations.

5) Honorarium and incentives

All participants will receive a gift. Transportation costs will be covered by the principal investigator of the study.

6) Potential risk to participant

All participants Fall or Injury Risk: Older adults may have weaker muscle strength, balance, and coordination, which makes them more prone to falls or injuries during rehabilitation activities. If participants fall or are injured during the intervention, necessary medical support will be provided.

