1) Research design: Quasi-Experimental Design (Non-randomized controlled trial) with experiment and control groups for comparison. Because of ethical considerations on older adults for logistical and economical wise, easy to travel, practical, less budget. Similar studies involving rehabilitation or behavioural interventions in real-world settings have widely used quasi-experimental designs. Studies by MA Handley(2018) and AD Harris (2006) demonstrated reliable outcomes using this approach.

2) Study area: Liaoning Province, China.

3) Study population

i) Reference population: Older adults living in Liaoning.

ii) Source population / sampling pool: Elderly care institutions and rehabilitation centers, Liaoning Province.

iii) Target population: Jinzhou Comprehensive Elderly Care Institution and Rehabilitation Center, Liaoning Province.

iv) Sampling frame: List of members from the two elderly care institution and rehabilitation center; Jinzhou Pension Comprehensive Service Center (JPCSC)), and Jinzhou Rehabilitation Hospital (JRH), Liaoning Province.

4) Subject criteria

Objective No. 1 and 2: To develop and validate the psychomotor rehabilitation nursing plan through content/face validation using the Delphi method.

Inclusion criteria:

- i) Professionals with ≥ 5 years of experience in geriatric care, neurological rehabilitation, cognitive rehabilitation, or psychomotor therapy.
- ii) Academic researchers with publications in related fields.
- iii) Intermediate professional title or above.
- iv) Willingness to participate in multiple Delphi rounds and provide informed feedback.

Exclusion criteria:

- i) Experts without sufficient relevant experience.
- ii) Those unable to commit to the Delphi process.

Objective No. 3: To evaluate the effectiveness of the psychomotor rehabilitation nursing plan in enhancing cognitive function among older adults with mild cognitive impairment. (Experimental and control group)

Inclusion criteria:

- i) Older adults are aged 50 years and above.
- ii) Subjective cognitive complaints from the individual or caregiver.
- iii) Screening for MCI using the Mini-Cog scores between 0-2 (SN Abayomi, 2024).
- iv) Basic language communication, listening, speaking, and understanding skills.

- v) Ability to provide informed consent.

Exclusion criteria:

- i) Diagnosed with severe psychiatric conditions (e.g., schizophrenia, major depressive disorder).

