- ii) It is at the end stage of important functional organ diseases, such as malignant tumors, cardiac failure, etc.
- iii) Limb dysfunction.
- iv) Diagnosed with dementia.

Withdrawal criteria:

- i) Withdrawal of consent by the participant.
- ii) Non-compliance with study requirements (e.g., missing >25% sessions).
- iii) Significant health deterioration affecting participation.

5) Study groups

Experimental group: Older adults with MCI from Jinzhou Rehabilitation Hospital (JRH), with psychomotor rehabilitation nursing plan.

Control group: Older adults with MCI from Jinzhou Pension Comprehensive Service Center (JPCSC), without psychomotor rehabilitation nursing plan.

6) Operational definition:

- i) Mild cognitive impairment (MCI): Mild Cognitive Impairment (MCI) is defined as a condition characterized by noticeable cognitive decline beyond what is expected for an individual's age and education level, but not severe enough to interfere significantly with daily life or independent functioning. It serves as an intermediate stage between normal aging and dementia. (Petersen, R.C., 2004; B. Winblad, 2004).
- ii) Psychomotor therapy (PMT): Psychomotor therapy is a form of therapeutic intervention that focuses on the connection between psychological and motor (physical) functions (Duan Zhouying, Chen Wenhua, 2021).

7) Sample size determination

Objective No. 1 and 2: To develop and validate the psychomotor rehabilitation nursing plan through content/face validation using the Delphi method for older adults with mild cognitive impairment in promoting cognitive function.

A sample size of 8 to 15 respondents has been recommended for Delphi studies, given that smaller samples reduce reliability and bigger ones do not appear to add much value (Kenney et al., 2010). For this study, we aimed to recruit 10-12 participants.

Objective No. 3: To determine the effectiveness of the psychomotor rehabilitation nursing plan in enhancing cognitive function among older adults with mild cognitive impairment .

The sample size was calculated for specific objective 2. It was estimated by using the sample size formula compared with the average of two samples (Ni Ping et al., 2010) . The sample size calculation formula and parameters were as below:

$$N1 = N2 = 2[(t_{\alpha/2} + t_{\beta})S/\delta]^2$$

N1 is the sample content of the experimental group.

N2 is the sample content of the control group.

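### The entry rules do not exclude cognitive impairment from a recent acute event, so natural recovery over 12 weeks could be counted as benefit of the psychomotor plan

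*Combined protocol and SAP*

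**What the plan says.** Section 4, Subject criteria, Objective No. 3, admits people aged 50 or over with "Subjective cognitive complaints from the individual or caregiver", a Mini-Cog score of 0 to 2, basic communication skills and the ability to consent. The exclusions are diagnosed severe psychiatric illness (major depressive disorder is one example), end-stage organ disease ("It is at the end stage of important functional organ diseases, such as malignant tumors, cardiac failure, etc"), "Limb dysfunction" and diagnosed dementia.

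Section 6, Operational definition, describes MCI as decline beyond what age and education would lead one to expect, and adds: "It serves as an intermediate stage between normal aging and dementia".

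Section 5, Study groups, ties arm to institution: "Experimental group: Older adults with MCI from Jinzhou Rehabilitation Hospital (JRH), with psychomotor rehabilitation nursing plan". All controls come from the pension service centre. Section 8 gives purposive sampling. Section 9, Phase 2, describes the participants as "older adults with MCI admitted in two China elderly care institutions".

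Section 10 has one assessment before the intervention and one at 12 weeks. Section 11, Objective No. 3, bases the comparison of scale scores on a paired t-test. The dummy tables are titled as comparisons between two groups, but their columns are before and after, each with n = 76.

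**The concern.** A complaint of any age and any cause satisfies the inclusion list. A person whose thinking worsened after an operation or infection some weeks earlier can meet every entry criterion, yet does not have the intermediate stage between normal aging and dementia that the plan sets out to treat. Part of such impairment may resolve without treatment during follow-up.

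The design has little with which to recognise this. A single baseline cannot show that the impairment was stable. Arm and institution coincide completely, so any difference between the sites in the share of recovering participants enters the arm comparison directly, and a larger sample would not remove it. At stake is whether a rise in MoCA at 12 weeks can be attributed to the psychomotor plan. The problem is separate from concurrent therapy at the hospital, because it would arise with no other treatment at all.

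**Working it through.** **Step 1. Entry rules against the plan's own condition.** Take impairment that began with a recent acute event and go through the rules:

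- Complaint and Mini-Cog 0 to 2: met. Neither asks about onset.
- Limb dysfunction: removes some post-stroke patients, not those without limb deficit.
- Diagnosed major depressive disorder: removes some depression-related impairment.
- Consent and communication: probably remove overt delirium, not milder after-effects.
- End-stage organ disease and diagnosed dementia: do not bear on a recent acute event.

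The exclusions therefore remove only part of these cases. The definition in section 6 does not close the gap, since no entry criterion puts it into practice on cause or duration.

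**Step 2. What the data form can recover.** Section 10 and the Data Collection Form in the appendices record age, sex, education, family history of dementia, marital status, income and chronic disease. Item 7 asks for the name of the disease, which may flag some vascular or neurological history. There is no onset date and no reason or date of admission. Adjustment would be incomplete.

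**Step 3. The plan's own figure.** Section 7 uses S = 2.75 and δ = 2.14, both MMSE values, with 1.96 and 1.28:

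2 × [(1.96 + 1.28) × 2.75 / 2.14]² = 34.67

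The plan states 34 per group (rounding up gives 35), and 38 after the 10% allowance (34 / 0.90 = 37.8). The figure reproduces closely enough for what follows.

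**Step 4. Illustration for a between-group test.** Assumptions that are not in the documents: no PMT effect; a fraction f more experimental than control participants are recovering; each gains g points; MoCA has the plan's MMSE SD; a two-sided two-sample t-test at 5%. The bias is b = f × g. With n per group, the noncentrality is b / (S√(2/n)). At n = 38, S√(2/38) = 0.631.

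Recovery in only a fraction of the arm also adds f(1 − f)g² to the experimental-arm variance. With 34 completers the standard error becomes √{[2S² + f(1 − f)g²] / 34}.

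| f | g | b | b / 2.14 | Rate, n = 38, SD 2.75 | Rate, n = 34, added variance |
|---|---|---|---|---|---|
| 10% | 2 | 0.2 | 9% | 6.1% | about 6% |
| 20% | 3 | 0.6 | 28% | 15.5% | about 14% |
| 30% | 3 | 0.9 | 42% | 29.1% | about 24% |
| 40% | 3 | 1.2 | 56% | 46.7% | about 38% |

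For the second row, the noncentrality is 0.6 / 0.631 = 0.951 at n = 38. At n = 34 the added variance is 0.2 × 0.8 × 9 = 1.44, the standard error is √[(15.125 + 1.44) / 34] = 0.698, and the noncentrality is 0.860.

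**Step 5. Illustration for the stated paired test.** The SD of change is S√[2(1 − r)], with an assumed pre-post correlation r of 0.5 to 0.8, so 2.75 down to 1.74. For 34 pairs in one arm, by normal approximation, a mean natural gain of 0.5 points is significant in 18.5% to 38.8% of trials, and a gain of 1.0 point in 56.4% to 91.8%. This needs no difference between the sites.

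**The case against.** The strongest objection is that the premise about the sites is undocumented. Nothing gives case mix, length of stay or reason for admission at either institution, section 9 calls both elderly care institutions, and section 3 samples from member lists of both. A reader might infer from the word hospital that recovery would fall mainly on the experimental arm. The documents do not support that as a fact, so the direction of any between-group bias has to stay conditional. The paired analysis needs no such premise.

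A reader might also infer that no later adjustment could help. That goes too far: named chronic disease and baseline MoCA are collected and could do part of the work. Neither dates the complaint or identifies an acute event.

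The calculation in step 4 is open to criticism too. It borrows MMSE values for a MoCA outcome, assumes a test the plan does not state, and uses fractions and gains with no anchor in the documents. At its low end the effect is negligible (6% against a nominal 5%). All of that stands, so the figures are illustrations only.

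Finally, this is one mechanism within the wider problem of allocation by institution, and correcting it leaves that problem in place. True, but it can be corrected separately and cheaply.

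**Conclusion.** The point holds as a gap in eligibility and data capture. The entry rules admit impairment that lies outside the plan's own definition of MCI, and the existing exclusions remove only part of it. As the analysis is written, natural recovery in either group would count as improvement. In a between-group comparison it would favour PMT only if such cases are commoner at the rehabilitation hospital, which is plausible and unverified.

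The size is unknown. The range of about 6% to 47% (38 per group), or about 6% to 38% (34 completers with the added variance), shows only how the false-positive rate would respond to assumed inputs. It is not an estimate for this trial. The change is worth making because it is inexpensive and because facts about onset that are not recorded at enrolment will be missing from the planned dataset.

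**What to change.** 1. Add one exclusion, checked from the records in the same way at both institutions: a cognitive complaint that began with, or within a fixed period after, an acute event such as stroke, head injury, operation, acute infection or delirium. The clinical investigators set the period and apply it identically at both sites. This should be done before enrolment or, if enrolment has begun (section 10 dates data collection from January 2025 and the document is dated February 2025), by protocol amendment.
2. Add three fields to the Data Collection Form: date of onset of the complaint (from records or caregiver, since participants' own recall may be unreliable), reason for admission and date of admission. Report them side by side for the two sites.
3. Pre-specify a sensitivity analysis of the between-group MoCA comparison that leaves out participants with onset inside a stated cut-off. Fix the cut-off before the data are seen. The between-group comparison has to be written into section 11 for this to apply.

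The cost is one exclusion line, three fields, a records check at screening and a somewhat smaller eligible pool at the rehabilitation hospital. The target of 38 per group does not change. Temporary causes without an acute event are not caught by the exclusion; the onset date at least makes recent ones visible.
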